2.1.2 Visit windows for data analysis

Visit windows will be used for the data analysis, as per the planned visits in the protocol. During the q12w/q8w phase, i.e., from Week 16 to Week 44, the treatment visit intervals will be determined by the investigator, based on the patient's disease activity.

Table 2-1 Assessment windows for scheduled visits

Analysis Visit	Week	Scheduled Day	Visit Window
Screening/Baseline	BL	1	-14 days to Day 1*
Week 4	4	28	Day 22 - 34
Week 8	8	56	Day 50 – 62
Week 12	12	84	Day 71 – 97
Week 16	16	112	Day 99 – 119
Week 20	20	140	Day 127 – 153
Week 24	24	168	Day 155 – 182
Week 28	28	196	Day 183 – 209
Week 32	32	224	Day 211 – 237
Week 36	36	252	Day 239 – 265
Week 40	40	280	Day 267 – 293
Week 44	44	308	Day 295 – 321
Week 48	48	336	Day 323 - 349

* Baseline measurement before the first treatment administration.

If study visit assessments and the corresponding treatment occur on separate days, a repeat safety check-up should be performed prior to treatment of the eye and results documented in the source documents. If any safety concern arises related to the study eye that, in the opinion of the investigator, may be further impacted by the study treatment or injection procedure, treatment needs to be cancelled. Injections are contraindicated in patients with active intraocular or periocular infections and in patients with active intraocular inflammation; therefore, the investigators should verify that these conditions are not present in the study eye prior to every injection. Any AEs must be recorded in the eCRF.

The injection procedure for brolucizumab will be performed according to local clinical practice. Injections will be administered by the investigator.

Data collected at unscheduled visits will not be used in 'by-visit' tabulations or graphs and will be presented in listings.

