## 8 Visit schedule and assessments

The Assessment Schedule for the study eye ([Table 8-1](#)) lists all of the assessments when they are performed. All data obtained from these assessments must be supported in the patient's source documentation. All data requested by eCRF must be entered in a timely manner (see [Section 11.1](#)).

A planned study visit schedule will be established at Screening/Baseline/Day 1 for all patients. All post-Baseline and/or subsequent scheduled visits will be calculated based on the Screening/Baseline/Day 1 visit date. During the q12w/q8w phase, from Week 16 to Week 44, the treatment visit intervals will be determined by the investigator, based on the patient's disease activity (see [Section 6.7.2](#)). All efforts should be made to adhere to all scheduled visits and assessments as outlined in the assessment schedule ([Table 8-1](#)).

A  $\pm 7$ -day visit window is allowed should the patient be unable to return per the scheduled visit. All efforts should be made to revert back to the planned visit schedule taking into consideration the restrictions on the minimum treatment interval for the study medication (brolocizumab).

Assessments can be performed on 2 consecutive days in which both days must occur within the  $\pm 7$  days visit window.

Treatment is intended to be administered on the day of the study visit, or if this is not possible, within 3 days after the study visit at which the per-protocol assessments took place. If study visit assessments and the corresponding treatment occur on separate days, a repeat safety check-up should be performed prior to treatment of the eye and results documented in the source documents. For all visits, efficacy assessments ([Section 8.3](#)) and safety assessments ([Section 8.4](#)) should be performed prior to any administration of study treatment.

Missed or rescheduled visits should not lead to automatic discontinuation.

If the COVID-19 pandemic limits or prevents on-site study visits, study treatment should not be administered and other study assessments may not be performed. Alternative methods of safety monitoring may be implemented. Depending on local regulations, site capabilities and patients' visit status in the study, phone calls or virtual contacts (e.g. teleconsult) can be performed for safety follow-up for the duration of the pandemic, until it is safe for the participant to visit the site again.

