2.1.1 General definitions

Study treatment: This is a single-arm study and all patients will be treated with brolucizumab 6 mg. Three loading injections (at Screening/Baseline/Day 1, Week 4 and Week 8), followed by maintenance treatment from Week 16/Week 20 up to Week 40/Week 44. The investigator can individualize treatment intervals depending on disease activity, to adjust patient's injection regimen.

Study treatment start and end date: Study treatment start date is defined as the first date study treatment is administered and recorded on the treatment administration record (DAR) electronic case report form (eCRF) page. Similarly, study treatment end date is defined as the last date of study treatment is administered and recorded on the study treatment completion CRF page.

Generally, study day 1 is considered as the day of inclusion of the patient. However in this study, treatment is intended to be administered on the same day or if this is not possible, within 3 days after the day of inclusion of the patient.

Study day will be calculated as (event date – study treatment start date + 1 day) for events that occurred on or after study treatment start date (e.g. visit, AEs). For events prior to study treatment start date (e.g. time since diagnosis), study day will be negative and calculated as (event date – study treatment start date).

Baseline and post-baseline: Baseline value refers to the value of the last non-missing measurement collected prior to administration of the first dose of study treatment (Screening or Baseline visit). Intraocular pressure (IOP) will be assessed in the study eye, pre-dose and post-dose at every injection. The last available assessment taken prior to the first IVT injection of study treatment is taken as the "Baseline" assessment.

A "post-baseline" value refers to a measurement taken after the first dose of study treatment. When assessments and treatments take place on the same day, treatment must occur after completion of the efficacy assessments and pre-injection safety measures (tonometry, slit lamp and fundus examinations). If study visit assessments and the corresponding treatment occur on separate days, a repeat safety check-up will be performed prior to treatment of the eye and

results documented in the source documents. More post-baseline safety measurements will be recorded in source document; visit window will be applied to OCT and IVT visits.

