TRT04	Short treatment window between treatment	Included in everything	0
TRT05	Treatment > 3 days after injection visit	Included in everything	0
TRT06	Injection given at Week 12	Excluded from PPS	2
TRT07	Q8W IVT out of window	Included in everything	0
TRT08	Q12W IVT out of window	Included in everything	0
TRT09	COVID-19 Drug supply change	Included in everything	0

Deviation ID	Description of Deviation	Exclusion in Analyses	Severity code
TRT10	COVID-19 Treatment not given	Included in everything	0
TRT11	Missed Injection loading phase	Excluded from PPS	1
TRT12	Missed Injection	Included in everything	0
TRT13	No Disease activity but injection is given	Included in everything	0
TRT14	Treatment admin prior effic/safty evaluation	Included in everything	0
TRT15	Treatment given at EOS	Included in everything	0
WITH01	Withdrew consent not discontinued	Excluded from FAS and PPS	1
OTHER01	Patient rescreened > once	Included in everything	0
OTHER02	Severe ICH-GCP non-compliance	Excluded from FAS and PPS	1
OTHER03	New ICF is missing-rescreened	Excluded from FAS and PPS	1
OTHER04	Mishandling IP	Included in everything	0
OTHER05	Temperature excursion IP administered	Included in everything	0
OTHER06	Treatment regimen wrongly adjusted	Included in everything	0
OTHER07	Missed mandatory visit	Excluded from PPS	2
OTHER08	Missed injection visit	Included in everything	0
OTHER09	FA out of window	Included in everything	0
OTHER10	Rescreen due to BCVA results	Included in everything	0
OTHER11	Rescreen >14days w/o screening procedure	Included in everything	0
			1
OTHER13	COVID-19 Missed visit	Included in everything	0
OTHER14	COVID-19 Visit not at site	Included in everything	0
OTHER15	COVID-19 Assessment changed	Included in everything	0
OTHER16	COVID-19 Discontinuation Included in everything		0
OTHER17	Efficacy assessment not done Excluded from PPS		2
OTHER18	Safety assessment not done Included in everything		0
OTHER19	BCVA not done correctly Included in everything		0
OTHER20	Visit window > 7 days Included in everything		0
OTHER21	Vital signs/safety call not done Included in everything		0
OTHER22	Imaging analyzed after WoC Included in everything		0

Table 5-2 Patient Classification

Analysis Set	Severity codes that cause a subject to be excluded
ENR	NA
FAS	1
FAS-EST	1
PPS	1,2 (All specified PD in Table 5.1 due to COVID)
PPS-EST	1, 2 (All specified PD in Table 5.1 due to COVID-19)
SAF	NA

6 Reference

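### The SAP's analysis windows do not match the protocol's ±7 days: some compliant Week 4 and Week 8 visits fall in no window, and the Week 12 primary window admits scans about two weeks off target with no planned check

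*SAP*

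**What the plan says.** Protocol section 8 gives every visit a tolerance of seven days either side: a ±7-day "visit window is allowed should the patient be unable to return per the scheduled visit". The same section fixes the anchor: "All post-Baseline and/or subsequent scheduled visits will be calculated based on the Screening/Baseline/Day 1 visit date".

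SAP Addendum section 2.1.2 says "Visit windows will be used for the data analysis, as per the planned visits in the protocol". Its Table 2-1 then lists Week 4 (Scheduled Day 28) as Days 22–34, Week 8 (56) as Days 50–62, Week 12 (84) as Days 71–97 and Week 16 (112) as Days 99–119. Section 2.1.1 adds that the "visit window will be applied to OCT and IVT visits", which brings in the OCT-A scans behind the primary endpoint.

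Section 2.1.1 also defines the day count: "Study day will be calculated as (event date – study treatment start date + 1 day". The first injection may be given on the inclusion day or "within 3 days after the day of inclusion of the patient".

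Two other provisions matter. Section 2.1.2 says "Data collected at unscheduled visits will not be used in 'by-visit' tabulations or graphs", but says nothing about a scheduled visit that lands between two windows. In Table 5-1, deviation OTHER20, "Visit window > 7 days", has severity code 0, so it removes nobody from the FAS or the PPS.

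**The concern.** A table said to follow the protocol's visits should at least hold every visit the protocol counts as on time. This one is too narrow at Weeks 4 and 8 and about twice as wide as ±7 days at Week 12, and no reason is given for the different widths.

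Two things are at stake. First, Weeks 4 and 8 are mandatory visits at which the protocol follows the lesion through the loading phase. CNV area, CSFT, fluid and BCVA are all tabulated by visit, so a compliant visit with no analysis visit has nowhere to go in those tables. It might also be unavailable to the LOCF sensitivity analysis in SAP section 2.5.1.

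Second, the protocol chose Week 12 because it expects peak efficacy then. A wide window mixes scans taken at quite different times after the third injection, and no planned analysis shows whether that matters. The PPS does not screen these scans out, and the PPS analysis runs only if the FAS and PPS differ by more than 10% of patients.

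**Working it through.** **Inputs.** Tolerance ±7 days and anchor on the Day 1 visit date (Protocol section 8); study-day formula and a lag of 0 to 3 days from Baseline visit to first injection (SAP section 2.1.1); windows (SAP Table 2-1).

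**Step 1: reproduce the table.** The Scheduled Day column is 7 × week: 28, 56, 84, 112. Offsets from it are:
- Week 4: 22 − 28 = −6, 34 − 28 = +6
- Week 8: 50 − 56 = −6, 62 − 56 = +6
- Week 12: 71 − 84 = −13, 97 − 84 = +13
- Week 16: 99 − 112 = −13, 119 − 112 = +7

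None is ±7. The column also disagrees with the SAP's formula. With lag L, a visit exactly w weeks after Baseline falls on study day 7w + 1 − L. For L = 0 that is 29, 57, 85 and 113, one day later than printed.

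**Step 2: compare ±7 days with Table 2-1.**

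| Visit | SAP window | ±7, study-day formula (L = 0) | Compliant days unassigned | ±7, printed Scheduled Day | Compliant days unassigned |
|---|---|---|---|---|---|
| Week 4 | 22–34 | 22–36 | 35, 36 | 21–35 | 21, 35 |
| Week 8 | 50–62 | 50–64 | 63, 64 | 49–63 | 49, 63 |
| Week 12 | 71–97 | 78–92 | none | 77–91 | none |
| Week 16 | 99–119 | 106–120 | 120 | 105–119 | none |

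Either way, 2 of 15 permitted days are unassigned at Week 4 and 2 of 15 at Week 8. Week 16 is short by 1 of 15, on the study-day formula only. A lag of 1 day gives the same result as the printed column. Lags of 2 and 3 days leave 2 and 3 early days unassigned at each of Weeks 4 and 8, and none at Week 16.

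The compliant days sit in, or next to, longer uncovered runs: Days 35–49, 63–70 and 120–126. Days 21 and below, before the Week 4 window opens, are also uncovered.

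**Step 3: the Week 12 window.** Days 71–97 span 27 days. Outside Days 78–92 are Days 71–77 (7 days) and 93–97 (5 days), 12 in all. The largest departure is 85 − 71 = 14 days on the formula, or 13 on the printed Day 84. With the full 3-day lag the target is Day 82 and the largest departure is 97 − 82 = 15.

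**Step 4: time from third injection to scan.** Take a Week 8 injection on any compliant day, 50–64:
- SAP window: 71 − 64 = 7 to 97 − 50 = 47 days
- Protocol window: 78 − 64 = 14 to 92 − 50 = 42 days

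These are extremes, pairing opposite edges of the two visits. The SAP window adds 7 days at the short end and 5 at the long end.

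**The case against.** The best defence is that analysis windows need not equal conduct windows. A wide primary window keeps data, and the study is descriptive with no hypothesis test. That is fair for Week 12 taken alone. It does not explain why Weeks 4 and 8 are narrower than the protocol allows, which no data-retention argument supports.

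Several stronger readings are tempting and should be resisted.
- **That the SAP discards gap visits.** It does not say so; only unscheduled visits are confined to listings. Exclusion is what follows if the table is applied literally. The established defect is a missing rule.
- **That timely primary data are lost.** They are not: Days 78–92, and Days 75–89 with a 3-day lag, lie wholly inside Days 71–97.
- **That Week 16 is materially affected.** At most one edge day is, under one convention. The disease-activity decision is made by the investigator at the visit, so analysis windows cannot alter it.
- **That every uncovered day counts.** Days 98, 154, 210, 238, 266, 294 and 322 also fall in no window, but each is more than 7 days off target on either count, so none is a compliant visit.
- **That the 3-day-lag case is typical.** A Week 4 visit on Days 19–21 is 18 to 20 days after the first injection, short of the protocol's 21-day minimum between loading doses if treatment were given the same day. The point does not rest on it.

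**Conclusion.** The mismatch is real. Under every day convention checked, the Week 4 and Week 8 windows leave some protocol-compliant visits unassigned, and the Week 12 window is far wider than ±7 days. The exact days depend on the anchor: 35–36 and 63–64 by the SAP's formula with injection on Day 1, or 21, 35, 49 and 63 from the printed column. The Week 16 shortfall (Day 120) depends on the formula.

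For the primary endpoint the issue is only that off-time scans are accepted, up to 13 or 14 days from target without a treatment lag, and that nothing planned tests their influence. A reader might infer that the Week 12 estimate is biased. The documents do not support that, because they give neither the distribution of visit dates nor the change in lesion area with time since injection. The number of patients affected cannot be computed either. This is worth correcting before analysis, but it does not undermine the design.

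**What to change.** 1. Set the Scheduled Day column in Table 2-1 to agree with the study-day formula: 29, 57, 85, 113 and every 28 days after.
2. Make the windows contiguous so that every protocol-compliant visit is assigned, and take the scheduled visit closest to target when two fall in one window. Splitting at midpoints would give Week 4 Days 16–43, Week 8 Days 44–71, Week 12 Days 72–99 and Week 16 Days 100–127, which hold all compliant visits for lags of 0 to 3 days.
3. Add one sensitivity analysis of the primary endpoint limited to Week 12 OCT-A within the protocol's ±7 days: Days 78–92 when the first injection is on Day 1, shifted by the lag otherwise.

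Step 3 is essential because step 2 repairs only the gaps. A Week 12 window of Days 72–99 still has 6 + 7 = 13 of its 28 days outside Days 78–92, against 12 now, and its longest injection-to-scan interval is 99 − 50 = 49 days, against 47.

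The cost is a SAP table edit and one extra output. No new data are needed, and patient management does not change.

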2.2 Analysis sets

Enrolled Analysis Set (ENR): The ENR set includes all patients who signed an ICF and are assigned patient numbers.

Full Analysis Set (FAS): The FAS comprises all patients to whom study treatment has been assigned and who received at least one IVT injection of study treatment.

Safety Set (SAF): The SAF set includes all patients who received at least one IVT injection of study treatment.

Per-Protocol Set (PPS): The PPS is a subset of patients in the FAS without PDs with impact. The list of PD criteria will be provided in edit checks specification (ECS) document.

Full Analysis Set Estimand (FAS-EST): The FAS-EST comprises all patients who are in the FAS and did not discontinue treatment in the entire study due to COVID-19.

Per-Protocol Set Estimand (PPS-EST): The PPS-EST is a subset of patients of the FAS-EST without PDs with impact.

When assessing the robustness of the overall efficacy conclusions, considerations will be given to the analysis based on the estimand using FAS-EST and PPS-EST. The expectation for comparing both estimands is to have similar conclusions. Inconsistencies in the results will be examined and discussed in the CSR.

2.3 Patient disposition, demographics and other baseline characteristics

2.3.1 Patient disposition

The FAS will be used to prepare the summary and ENR will be used for listing of patient disposition.

The number and percentage of patients who completed the study and discontinued from the study will be summarized with reasons for premature discontinuation for the ENR. In addition, the number of screen failures with reasons will be presented for all screened patients. The patient identification number and whether patients completed or discontinued from the study will be listed, with date of last dose and primary reason for premature discontinuation.

A separate summary of disposition and listing for rescreened patients will be presented for the ENR.

Study treatment will be discontinued under the following circumstances:

- Adverse event
- Death
- Lost to follow-up
- Physician decision
- Pregnancy
- Progressive disease
- Protocol deviation
- Study terminated by sponsor
- Technical problem
- Patient decision
- New therapy for study indication
- Lack of efficacy
- Use of prohibited treatment
- Any situation in which study participation might result in a safety risk to the patient

2.3.2 Protocol deviation

The number and percentage of patients with protocol deviations will be tabulated by category and deviation for the FAS. Patients with protocol deviations will be listed with date and study day of occurrence, deviation and severity codes for the ENR.

The number of patients included in each analysis set will be tabulated for all enrolled patients. Reasons for exclusion from analysis sets will be tabulated for the ENR. Patient exclusion from analysis sets will be listed for all patients with reasons for exclusion (i.e., both protocol and non-protocol deviations).

2.3.3 **Demographic characteristics**

Demographic and Baseline characteristics will be listed and summarized descriptively for overall patients on FAS and Safety Set.

The following demographic and vital signs variables collected in the eCRF at Baseline will be summarized:

- Sex (male, female)
- Age (in years)

Novartis

- Age category ($< 50, 50 65, 65 75, 75 85, \ge 85$)
- Study eye (left [OS], right [OD])
- Vital signs (sitting systolic/diastolic blood pressure [mmHg], sitting pulse rate [bpm]) only on the days study treatment is administered, it is measured prior study treatment

2.3.4 **Baseline characteristics**

The following Baseline characteristics collected in the eCRF at Baseline will be summarized for study eye and fellow eye (wherever applicable):

- Time since nAMD diagnosis
- Time since nAMD diagnosis (< 1 month, 1-3 months and > 3 months)
- Unilateral versus bilateral nAMD
- BCVA
- BCVA ($\leq 55, 56 70, \geq 71$)
- BCVA categories (count fingers, hand motion, light perception, no light perception) in case BCVA score is 0
- FA (analyzed by Vienna [CRC])
 - 1. Lesion type (only at Baseline) (predominantly classic, minimally classic, occult)
 - 2. Lesion type (only at Baseline) (type 1 / type 2 / type 3 / type 1 with aneuvrism / polyps)
 - 3. CNV location (subfoceal, juxtafoveal, extrafoveal)
 - 4. Area of lesion associated with CNV (mm²)
- ICG (analyzed by Vienna [CRC])
 - 1. Lesion type (only at Baseline) (type 1 / type 2 / type 3 / type 1 with aneuvrism / polyps)
 - 2. Area of lesion associated with CNV (mm²)
- SD-OCT (analyzed by Vienna [CRC])
 - Lesion type (only at Baseline) (type 1, type 2, type 3)
 - CSFT (µm)
 - Baseline CSFT ($< 300, \ge 300 450, \ge 450 < 650, \ge 650 \text{ [}\mu\text{m}\text{]})$
 - Presence of fluid (YES/NO)
 - 1. Intraretinal fluid
 - 2. Subretinal fluid
 - 3. Sub-RPE fluid
 - Volume (mm³) and height (μm) of each fluid (in case of presence)
 - 1. Intraretinal fluid

- 2. Subretinal fluid
- 3. Sub-RPE fluid
- In case of sub-RPE / PED : nature : serious PED / fibrovascular PED / mixed PED
- OCT-A (analyzed by Vienna)
 - 1. CNV location (only at Baseline)
 - 2. CNV lesion area (at the biggest surface) (mm²/µm²)
- Fundus observation
 - 1. Retinal hemorrhage (none, retinal macular and retinal non-macular)
 - 2. Presence of vitreal hemorrhage (Yes, No)
 - 3. Retinal tear/ detachment (none, tear, detachment, both)
- Color fundus photography (CFP)
 - 1. Presence of retinal or subretinal hemorrhage (Yes, No)
 - 2. Presence of fibrosis (Yes, No)
 - 3. Presence of atrophy (Yes, No)
 - 4. Subretinal blood affecting foveal center point and/ or > 50% of total lesion (Yes, No)
- Fundus autofluorescence (FAF)
 - 1. Presence of macular atrophy (Yes, No)
 - 2. Area of macular atrophy
- Intraocular pressure
- Intraocular pressure (≤ 10 , 10-25, 25-30 and ≥ 30 [mmHg])
- Disease activity assessment (Present)
- History of primary diagnosis:
 - 1. Disease (neovascular age-related, macular degeneration [nAMD])
 - 2. Age of diagnosis
 - 3. Eye (OD, OS)
 - 4. Ongoing (Yes, No)
- History or evidence of the following in the study eye within the 90-day period prior to Screening/Baseline:
 - 1. Intraocular or refractive surgery
 - 2. Previous panretinal photocoagulation
 - 3. Previous submacular surgery, other surgical intervention or laser treatment for nAMD including photodynamic therapy (PDT)
- Concomitant medication at Baseline
- Medical history
- Co morbidities

2.3.5 Relevant medical history / current medical condition

Medical history / current medical conditions (general and ocular) will be coded using the Medical Dictionary for Regulatory Activities (MedDRA) terminology. History/conditions will be summarized for the FAS by primary system organ class (SOC), preferred term (PT) by eye (any eye, study eye and fellow eye). Verbatim recorded history/conditions will be listed together with the coded terms, date of diagnosis/surgery and whether the problem was ongoing at start of the study. The ongoing medical history will be considered as co morbidities. The co morbidities will be summarized and listed separately for eye (any eye, study eye and fellow eye and both eye).

